1. BACKGROUND AND SIGNIFICANCE

The endothelium provides a permeability barrier for the vasculature, maintains a nonthrombogenic surface, regulates vascular tone and tissue flow, and inhibits vascular smooth muscle cell growth. In the presence of inflammatory cytokines, endothelial cells are activated which facilitates leukocyte adhesion and migration into the vessel wall, production of prothrombotic substances, and vasoconstriction, thereby creating a proatherogenic and procoagulant environment. Consequently, inflammation is a key mediator of a constellation of abnormalities that initiate and accelerate the progression of atherosclerosis.

HIV-specific immune dysregulation promotes endothelial and immune cell activation. Indeed, antiretroviral (ART)-naïve HIV positive patients have higher levels of endothelial immune activation markers (e.g., IL-6, VICAM-1 and others) than non-HIV controls. ART-naïve HIV positive patients also show evidence of endothelial-cell dysfunction, as assessed by brachial artery reactivity. Treatment with ART has been shown to reduce biomarker evidence of endothelial cell activation in observational and randomized trials, and some of these drugs also appear to improve endothelial function. However, most prior evidence of the direct biologic effect of HIV viral infection and its changes with therapy on coronary vascular function has been indirect through the measurement of circulating biomarkers or brachial artery reactivity.

Positron emission tomography (PET) imaging allows precise and reproducible quantification of myocardial blood flow, thereby providing a direct assessment of coronary vascular health. Coronary flow reserve (CFR, calculated as the ratio of peak hyperemic myocardial blood flow over that at rest) is emerging as a powerful quantitative prognostic imaging marker of clinical cardiovascular risk. CFR provides a robust and reproducible clinical measure of the *integrated* hemodynamic effects of epicardial coronary artery disease (CAD), diffuse atherosclerosis, vessel remodeling, and microvascular dysfunction resulting from endothelial cell dysfunction on myocardial tissue perfusion across the entire coronary circulation. These processes have direct relevance to the underlying vascular pathobiology in patients with HIV infection. Consequently, quantitative CFR provides a unique opportunity to examine the potential impact of novel therapies on the biology of the disease and its association with cardiovascular outcomes. By testing the fundamental concept of whether novel ART therapies in HIV can lead to improved coronary blood flow and myocardial tissue perfusion, TAF-CFR would provide important mechanistic insights of the capabilities of TAF therapy to improve key determinants of clinical risk.

JUSTIFICATION FOR THE USE OF CFR AS A SURROGATE MARKER OF CLINICAL RISK

Noninvasive quantification of coronary flow reserve improves diagnosis and risk assessment in non-HIV patients with CAD. Noninvasive quantification of coronary blood flow and flow reserve has been the research focus of our group for over 20 years. Our group has developed and validated methodology for flow quantification and disseminated this technology for broad access and use. We and others have demonstrated that CFR is a quantitative unique phenotyping tool to assess vascular health and pre-clinical atherosclerosis which, in higher risk patients, can reveal flow-limiting coronary artery stenosis, thereby improving the accuracy of myocardial perfusion imaging in the diagnostic evaluation of known or suspected CAD¹⁻⁴. More recent data support the notion that coronary vascular dysfunction, as quantified by reduced CFR, is highly prevalent among patients with known or suspected CAD^{2,5}, increases the severity of inducible myocardial ischemia (beyond the effects of upstream coronary obstruction)⁶ and sub-clinical myocardial injury⁷, and identifies patients at high risk for serious cardiac adverse events, including cardiac death⁸⁻¹¹. Thus, CFR is a robust measure of the *integrated* hemodynamic effects of epicardial CAD, diffuse atherosclerosis, vessel remodeling, and microvascular dysfunction on myocardial perfusion. In the presence of increased oxygen demand, a decreased CFR

reflects an imbalanced supply-demand relationship that may lead to myocardial ischemia, subclinical LV systolic and diastolic dysfunction, clinical symptoms and, ultimately, death. There is also emerging evidence that a reduced global CFR may help identify patients who benefit most from revascularization¹².

Systemic inflammation is associated with coronary vascular dysfunction. There is increasing evidence that coronary vascular dysfunction is associated with systemic inflammation and may precede or coexist with high-risk coronary atherosclerosis. Compared to healthy subjects, patients with rheumatoid arthritis or systemic lupus erythematosus, without significant CAD on invasive angiography, have impaired CFR to a degree directly related to disease duration¹³. In patients with cardiac syndrome X (CSX) with exertional angina and ST-segment depression on exercise stress testing but normal luminal coronary angiography, only those with elevated high sensitivity C-reactive protein (hsCRP, >3 mg/L) have reduced CFR¹⁴. Among patients presenting with acute coronary syndrome and nonobstructive CAD by angiography, reduced CFR (assessed by invasive Doppler flow velocity monitoring) is associated with higher frequency of thin-cap fibroatheroma, greater plaque burden, and significantly higher levels of hsCRP, despite similar amounts of epicardial disease by luminal area and fractional flow reserve measurements¹⁵. These results reinforce previous observations¹⁶⁻¹⁸ that inflammation is associated with impaired coronary vasoreactivity and, in the appropriate patient population, may be a better marker for poor outcomes related to diffuse and/or microvascular CAD than are conventional ischemic assessments.

Anti-inflammatory therapies can modulate CFR. There is preliminary evidence that anti-inflammatory therapies lead to improved CFR. Indeed, treatment with statins in patients with dyslipidemia has been shown to improve CFR in a way that is modified among carriers of a specific polymorphism that reduces IL-1beta expression¹⁹. Short-term inhibition of IL-1 activity with the IL-1 receptor antagonist anakinra in rheumatoid arthritis patients without perfusion abnormalities has been shown to improve echocardiographic measures of LV myocardial deformation (by speckle tracking) and CFR (by Doppler flow velocity in the left anterior descending artery (LAD))²⁰. Finally, treatment with methotrexate led to reduced clinical scores of disease severity and improved CFR (as measured by echo Doppler flow velocity in the LAD) in patients with early rheumatoid arthritis, with no effect on common carotid intima-medial thickness²¹.

Coronary vascular dysfunction is a powerful predictor of clinical risk. Emerging data have consistently shown that CFR measurements by PET can distinguish patients at high risk for serious adverse events, including cardiac death⁸⁻¹¹. We recently reported that reduced global CFR is independently associated with higher rates of cardiac and all-cause mortality in a large cohort of patients with and without DM^{8, 22}. Relatively preserved CFR identifies patients with known or suspected CAD who have significantly lower risk of cardiac death, regardless of traditional semi-quantitative measures of stress-induced ischemia. Conversely, reduced CFR identifies patients at significantly higher risk of cardiac death, even among those without objective evidence of ischemia, probably due to diffuse atherosclerosis and/or microvascular dysfunction. PET measures of CFR improved risk stratification beyond comprehensive clinical assessment, LVEF and semi-quantitative measures of myocardial ischemia and scar, and led to clinically meaningful risk-reclassification of ~50% of intermediate risk patients⁸. Diabetics with impaired vs. preserved CFR experienced substantially higher cardiac mortality (7.6%/year vs. 1.3%/year, relative to 4.2%/year vs. 0.4%/year in nondiabetics, respectively, both $p < 0.0001$)²². Importantly, diabetic patients without known CAD and with impaired CFR experienced a rate of cardiac death comparable to, and possibly higher than, that for nondiabetic patients with known CAD (Fig. 3). Measures of CFR integrate the hemodynamic effects of focal epicardial coronary stenosis, fluid dynamic effects of diffuse atherosclerosis, and the effects of coronary microvascular dysfunction, all of which are prevalent among diabetics²³⁻²⁵, and affected by systemic inflammation. These observations have implications for the

classification of DM as a coronary disease risk equivalent²⁶. *Specifically, only among diabetics with impaired vascular function is prognosis comparable to nondiabetic patients with known CAD.* Thus, differing levels of vascular health among previously studied cohorts may account for inconsistencies in relative mortality rates of diabetics without CAD and nondiabetics with CAD²⁷⁻²⁹.

Quantitative CFR is a modifiable imaging biomarker of disease. There is consistent evidence supporting quantitative CFR as a powerful marker of vascular health and, as such, a useful marker to improve diagnosis and risk stratification and to monitor response to treatment, particularly in the context of clinical trials. The accuracy of quantitative noninvasive PET measures of myocardial blood flow and flow reserve by PET has been extensively validated in experimental animals³⁰ and humans³¹⁻³⁴. The reproducibility of this technique is also well-established^{33, 34}. PET is considered *the gold standard* for quantifying coronary blood flow and flow reserve. There is extensive data supporting its use in diagnosis of CAD^{4, 35-37}. *The data discussed above demonstrate that the presence of abnormal CFR as measured by PET provides incremental risk stratification that leads to significant and meaningful risk-reclassification of intermediate risk patients^{5, 9-11}, especially those with DM²².* Furthermore, quantitative CFR as a measure of coronary vascular dysfunction is a *modifiable* imaging biomarker, which has been tested in the context of clinical trials^{19, 38-46}.

Abacavir is a nucleoside reverse transcriptase inhibitor used as part of treatment regimens for HIV. An association between abacavir and increased myocardial infarction was first reported in 2008⁴⁷. Since then, most but not all studies have had similar findings⁴⁸. As a result, HIV treatment guidelines state that ABC should be used with caution in patients with CV disease or at high CV risk. While the mechanism by which ABC increases CV risk is not definitively known, hypotheses include its effect on platelet aggregation, leukocyte adhesion, and systemic inflammation⁴⁸.

Bictegravir/emtricitabine/tenofovir alafenamide (B/F/TAF) is a single pill regimen that was approved by the FDA in February 2018 for treatment of HIV. The marketed name of the drug is Biktarvy. In two phase 3 comparative clinical trials, including one with ABC/3TC/DTG, it was found to be non-inferior to dolutegravir-containing regimens in terms of virologic outcomes^{49, 50}. B/F/TAF was also well tolerated, with few discontinuations for adverse events. As a result, B/F/TAF is an ideal non-abacavir containing regimen to assess the effect of removing ABC on coronary flow reserve.

2. SPECIFIC AIMS

2.1 Hypothesis and Objectives

The *primary hypothesis* of the B/F/TAF-CFR study is that reducing endothelial cell activation and dysfunction using *bictegravir/Emtricitabine/Tenofovir Alafenamide (B/F/TAF)* in place of abacavir/lamivudine/dolutegravir (ABC/3TC/DTG) will quantitatively improve coronary flow reserve as measured by PET over 24 weeks, in stable higher risk asymptomatic patients with HIV.

The primary objective of the B/F/TAF-CFR study is to test the hypothesis that in stable HIV patients treated with abacavir/lamivudine/dolutegravir STR regimens, a switch to a single tablet regimen (B/F/TAF) will improve coronary flow reserve and myocardial tissue perfusion, as assessed by quantitative PET imaging. This is a prospective, single arm study in which we will test that treatment B/F/TAF orally daily for 24 weeks will result in improved global coronary flow reserve in response to adenosine, reflecting coronary vasodilator function, as compared to baseline.

2.2 Primary Endpoint:

Change (from baseline) in global coronary flow reserve, as measured by PET imaging at 24 weeks after initiation of B/F/TAF therapy.

2.3 Secondary Endpoints:

- 2.3.1. Change (from baseline) in peak-stress global myocardial blood flow (in mL/min/g) at 24 weeks after initiation of B/F/TAF;
- 2.3.2. Change (from baseline) in peak-stress global coronary vascular resistance (in mm Hg/mL/min/g) at 24 weeks after initiation of B/F/TAF;
- 2.3.3. Change in serum biomarkers of inflammation (hs-CRP, IL-6, sCD163 and sCD14), myocyte injury and strain (hs Troponin, NT-proBNP) at 24 weeks after initiation of B/F/TAF.

3. SUBJECT SELECTION

3.1. Study Design

Open label, multicenter, uncontrolled, single arm pilot study. Patients with stable HIV currently treated with abacavir/lamivudine/dolutegravir STR regimens will be eligible for the B/F/TAF-CFR study. PET scans will be performed after enrollment while on the abacavir/lamivudine/dolutegravir STR regimen and at 24 weeks after the switch to B/F/TAF regimen. Patients will be encouraged to remain on stable medical therapy throughout the enrollment period.

3.2. Study group: HIV patients on stable therapy with abacavir/lamivudine/dolutegravir STR regimens.

3.2.1. Inclusion criteria:

We will recruit patients with HIV on abacavir/lamivudine/dolutegravir STR regimens for at least 1 year fulfilling the following inclusion criteria:

- (1) age \geq 45 years for men and \geq 55 years for women;
- (2) at least one coronary risk factor including smoking, dyslipidemia, hypertension, obesity (BMI $>$ 30) or diabetes, or a calculated 10-year risk of heart attack of 7.5% or higher;
- (3) HIV RNA $<$ 200 copies/mL at last clinical measurement, done within the past 12 months prior to screening, with no intervening HIV RNA $>$ 200;
- (4) Screening HIV RNA $<$ 50 copies/mL, HGB $>$ 10 g/dl, or Glomerular Filtration Rate (GFR) $>$ 30 that do not preclude the use of Biktarvy.

3.2.2. Exclusion criteria:

- (1) patients not fulfilling inclusion criteria;
- (2) unstable HIV disease or other medical condition that, in the opinion of the investigator, would interfere with the conduct of the study;
- (3) history of cardiomyopathy (LVEF $<$ 40%) or significant valvular heart disease;
- (4) cirrhosis;
- (5) end stage renal disease on dialysis;
- (6) uncontrolled hypertension (defined as SBP $>$ 200 or DBP $>$ 110);
- (7) pregnancy and breast-feeding;

- (8) Patients requiring medications contraindicated with the components of B/F/TAF;
- (9) Patients on active treatment for severe asthma or severe COPD;
- (10) Hepatitis B;
- (11) Any reported use of methamphetamine, cocaine and heroin within the past 6 months; if such use has been reported, a negative toxicology screen will be required before entry.

3.2. Source of subjects and recruitment methods

A total of 30 evaluable patients will be required. This will be a collaborative effort between 4 sites in the Boston area: (1) *Brigham and Women's Hospital, BWH* (PI: [name]), (2) *Boston Medical Center* (PI: [name]), (3) *Tufts Medical Center* (PI: [name]), and (4) *Massachusetts General Hospital* (PI: [name]). All patients will be referred for PET imaging to BWH, with BWH serving as the Core Imaging Lab and Data Coordinating Center (PI: [name] [name]).

4. SUBJECT ENROLLMENT

4.1. Procedures for obtaining informed consent

The Principal Investigator, co-investigator, or qualified PI designee at each site will obtain consent during the study-related hospital visit prior to any study-related procedures. Consent of subjects who do not speak English will be obtained and documented following the procedures outlined by IRB policy at each recruiting site. The informed consent process will also be documented and added to the research files for this study.

4.2. Methods of Enrollment

Potential study subjects will be recruited from medical clinics at BWH, MGH, BMC, and Tufts Medical Center. Screening procedures will include queries for potentially eligible subjects from lists of patients who are followed at each site. Investigators at each site will evaluate whether a patient might be a candidate for the study and follow site-specific protocols for approaching patients and invite them into the study. We will make every effort to mitigate any undue influence on patients to participate in this study, including providing the informed consent document to the patient to take home. The patient will then be instructed to reach out to the study team or other healthcare providers with questions at any time. The PI or PI designee at each site will review the informed consent form with the patient and answer any additional question the patient may have. All PET/CTs will occur at BWH. Treatment assignment and monitoring will be performed by each site. Additional procedures, particularly at the Baseline and End of Treatment visits may be performed at the local site or at BWH, for the convenience of the subjects.

4.3. Treatment assignment

Study subjects will all receive one tablet daily of bicitgravir 50 mg/emtricitabine 200 mg/tenofovir alafenamide 25 mg.

5. STUDY PROCEDURES

5.1. Study visits and parameters to be measured

This is a collaborative, multi-center, single arm trial. After giving written informed consent to participate in the study and fulfilling criteria for inclusion, patients will be switched to B/F/TAF and followed up for 24 weeks. Patients will undergo rest and vasodilator-stress PET/CT scan for measurement of coronary flow reserve at baseline (before the switch to B/F/TAF), and again after completion of 24 weeks of B/F/TAF. Safety labs will be assessed at baseline at the 45-day study visit and at the end of the study at the Day 168 visit. There will be follow up phone calls at day 14, day 126, and one week after the end of study at day 174. Follow up calls will be used to assess changes in medical history and for any adverse event.

Figure 1. Outline of Procedures

[figure not shown]

Table 1. Schedule of Assessments

Procedure	Screening (-28 to -1 days)	Baseline (day 0)	Tel F/U 1 (day 14)	Study Visit (day 45)	Tel F/U 2 (day 126)	End of Treatment (day 168)	Tel F/U 3 (day 174)
Informed Consent	X						
Inclusion/Exclusion Criteria	X	X					
Demographics		X					
Medical History		X	X	X	X	X	X
Medication History		X	X	X	X	X	X
Vital Signs	X	X		X		X	
Physical Exam		X		X		X	
Pregnancy Test ⁺	X	X				X	
Lab Tests (Clinical)	X	X		X		X	
Lab Tests – Research Only (to store)		X				X	
ECG		X				X	
PET/CT		X				X	

Study Drug Dispensed		X		X			
Study Drug Pill Count / Diary Collection				X		X	
AE Monitoring		X	X	X	X	X	X

***Telephone follow-up calls and study visits will be +/- 7 days to allow for scheduling flexibility.**

****Day 45 study visit will be +/- 14 days to allow for scheduling flexibility.**

*****Day 168 study visit will be +/- 7 days to allow for scheduling flexibility and to ensure adequate supply of study drug.**

+Screening Pregnancy test may be urine or serum

Screening (-28 to -1 days)

- All screening assessments will occur within 28 days prior to start of medication switch
- Obtain informed consent
- Note whether subjects have fasted for 4 hours prior to the visit
- Review inclusion and exclusion criteria to ensure the patient is eligible
- Obtain vital signs, including weight and height, systolic and diastolic blood pressure (BP), heart rate (HR)
- Perform laboratory tests, including pregnancy test (if WOCBP) and hepatitis B. Laboratory tests (excluding pregnancy is WOCBP) are valid within one year of the screening visit).

Baseline (Day 0, just prior to study medication initiation)

- Verify clinical stability since screening evaluation
- Confirm that subjects have withheld caffeine for 12 hours and fasted for 4 hours prior to imaging tests
- Confirm that subjects have withheld beta blockers, calcium channel blockers and arterial vasodilators for 24 hours prior to the PET scan
- Obtain interim medical history and concomitant medications review
- Obtain vital signs, including weight and height, systolic and diastolic blood pressure (BP), heart rate (HR), and oxygen saturation (O₂ sat)
- Obtain 12-lead ECG
- Complete physical exam
- Perform laboratory tests, including serum pregnancy test prior to any imaging
- Perform PET/CT scan
- Study medication initiation must occur *within 10 days* of the baseline evaluation
- Provide subjects with study drug and diary to take until next study visit (Day 45)
- Monitor for AEs. Educate patients on most common side effects of the new drug (Table 3). They are encouraged to immediately contact study investigators/staff by email and/or phone for any new or concerning symptoms.

Day 14 (Telephone follow-up call 1)

- Contact all subjects by telephone approximately 2 weeks after medication switch
- Assess changes in medical history or medication changes
- Monitor for AEs

Day 45 (study visit)

- Assess drug compliance via pill count
- Verify clinical stability since screening evaluation
- Confirm that subjects have fasted for 4 hours prior to imaging tests
- Obtain interim medical history and concomitant medications review
- Obtain vital signs, including weight and height, systolic and diastolic blood pressure (BP), heart rate (HR), respiratory rate (RR), and oxygen saturation (O₂ sat)
- Complete physical exam
- Perform laboratory tests
- Collect drug remaining study drug and first diary to assess compliance
- Prior to leaving, patients will be supplied with study drug and a new drug diary
- Monitor for AE; subjects are again educated about the most common side effects. They are encouraged to immediately contact study investigators/staff by email and/or phone for any new or concerning symptoms.

Day 126 (Telephone follow-up call 2)

- Contact all subjects by telephone approximately 18 weeks after medication switch
- Assess changes in medical history or medication changes
- Monitor for AEs

Day 168 (End of Treatment)

- Assess drug compliance via pill count
- Verify clinical stability since screening evaluation; including specific inquiry regarding common dose-related side effects associated with B/F/TAF
- Confirm that subjects have withheld caffeine for 12 hours and fasted for 4 hours prior to imaging tests
- Confirm that subjects have withheld beta blockers, calcium channel blockers and arterial vasodilators for 24 hours prior to the PET scan
- Obtain interim medical history and concomitant medications review
- Obtain vital signs, including weight and height, systolic and diastolic blood pressure (BP), heart rate (HR), and oxygen saturation (O₂ sat)
- Obtain 12-lead ECG
- Complete physical exam
- Perform laboratory tests, including serum pregnancy test prior to any imaging
- Collect remaining study drug and second drug diary to assess compliance
- Perform PET/CT scan

- Monitor for AEs

Day 174 (Telephone follow-up call 3)

- All patients will be contacted by telephone at approximately 7 days following administration of the last dose of study drug for AE monitoring.

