5.5. Data to be collected and timing of data collection

At each of the study visits, a medical history with symptom assessment, medication review, vital signs, physical exam, and blood samples will be obtained. As described above, additional data from the PET/CT scan as well as EKG assessment will be obtained at baseline and at the end of treatment period. One week after completion of the trial, telephone follow-up will be conducted to assess for any adverse events.

Laboratory analysis: Clinical labs will be collected at the Screening, Baseline, Day 45, and End of Treatment visits as follows:

- Screening: Comprehensive metabolic panel, lipid panel, hs-CRP, HbA1c, CBC, HIV RNA, D-Dimer, Hepatitis B Surface Antigen
- Baseline: hs-troponin and NT-proBNP
- Day 45: Comprehensive metabolic panel, lipid panel, hs-CRP, HbA1c, CBC, HIV RNA, D-Dimer

- End of Treatment: Comprehensive metabolic panel, lipid panel, hs-CRP, HbA1c, CBC, HIV RNA, D-Dimer, hs-troponin, NT-proBNP
- In addition, pregnancy tests will be performed (for women of child-bearing potential) at Screening and before each PET scan.

6. BIostatistical Analysis

6.1. Identification of clinical sites participating in the proposed ancillary study. BWH, MGH, Boston Medical Center and Tufts Medical Center will participate in this pilot study.

Based on the power calculations above and assuming a 20% effect size, the study will need to recruit approximately 30 patients, approximately 10 patients per site. BWH may recruit up to 20 patients. We believe that the proposed study is reasonable and attainable. [name] is an experienced clinical investigator with a successful track record in HIV clinical trials. [name] is a recognized expert in quantitative PET and nuclear cardiology imaging, has published widely on these topics, and has extensive experience in conducting clinical trials using imaging endpoints⁵¹⁻⁵⁴.

6.2. Power Analysis:

The table below shows the sample size needed to reach 85% power for an effect size of 20-30% relative improvement in coronary flow reserve from baseline using a standard deviation of 0.7 at baseline and follow-up and a correlation of 0.7 between baseline and follow-up measurements. Effect sizes were calculated from a baseline mean CFR of 1.74, which is a conservative value derived from our previous measurement of CFR in patients with HIV referred for myocardial perfusion imaging with PET:

Table 2. Power calculation

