9. MONITORING AND QUALITY ASSURANCE

9.1. Safety monitoring

The PI of the study will monitor the overall safety of the study and will report any adverse events to the IRB, per local institutional guidelines. The PI will also monitor this study to ensure that subjects' human rights, safety, and well-being are protected, that the study is properly conducted in adherence to the current protocol, and study data reported by the investigator/subinvestigator are accurate, complete and verifiable with study-related records such as source documents.

Safety data will be obtained at each study visit from the spontaneous reports by patients of adverse events, vital sign monitoring, physical examinations, 12-lead ECGs and clinical laboratory tests. In addition, telephone follow-up will be conducted to assess for any adverse events. All safety data will be reviewed by an HIV physician investigator ([name]).

Patients with unexpected abnormalities on the baseline PET scan will be discussed with the patient's PCP/ID physician to decide whether the patient should participate in this pilot trial. The findings will be discussed with the patient and the patient's primary physician in order to facilitate an appropriate management plan. If a patient is excluded on safety grounds, we do not think that this will affect our ability to determine the effect of B/F/TAF on myocardial blood flow.

The safety of B/F/TAF will be assessed with respect to the following end points: (1) death from any cause, (2) the composite of death from any cause or any cardiovascular hospitalization, (3) frequency of symptomatic documented arrhythmia, (4) serious adverse events related to the study drug and clinically significant laboratory abnormalities.

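### The B/F/TAF-specific side-effect inquiry is specified only at Day 168, so common non-serious adverse events are ascertained unevenly and have no matching pre-switch answer

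*Combined protocol and SAP*

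**What the plan says.** Section 5.1 lists a check of clinical stability since screening at Baseline, Day 45 and Day 168. Only the Day 168 item goes further, "including specific inquiry regarding common dose-related side effects associated with B/F/TAF".

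Other contacts are not silent on symptoms. Section 5.5 states: "At each of the study visits, a medical history with symptom assessment". Baseline, which precedes the first B/F/TAF dose, also has this item: "Obtain interim medical history and concomitant medications review". On the telephone contacts, section 5.1 says: "Follow up calls will be used to assess changes in medical history and for any adverse event". The first call is made to everyone: "Contact all subjects by telephone approximately 2 weeks after medication switch". Its list then reads "Assess changes in medical history or medication changes", followed by adverse-event monitoring. Patients are taught the common side effects at Baseline and again at Day 45, and are told to contact staff about new or concerning symptoms.

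Section 9.1 describes visits differently: "Safety data will be obtained at each study visit from the spontaneous reports by patients of adverse events". That sentence goes on to name vital signs, examinations, ECGs and laboratory tests, and the next one adds the telephone follow-up.

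Section 9.4.1 defines an adverse event by its timing relative to study drug. It has no rule for a symptom already present before the switch.

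**The concern.** The trial is open label and uncontrolled, so the patient's state on ABC/3TC/DTG is the only reference for tolerability on B/F/TAF. If the pointed question is asked only at the end, three things can follow.

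- A symptom carried over from the old regimen may first be named at Day 168 and be recorded as arising on B/F/TAF.
- A mild symptom in the first weeks that has resolved may go unrecorded unless general questioning draws it out or the patient recalls it months later.
- A patient who stops before Day 168 may never be asked.

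The missing pre-switch answer also limits what can be said in the drug's favor. Section 5.2 cites less nausea on B/F/TAF than on ABC/3TC/DTG. Without the same question before the switch, the trial has no like-for-like measure of whether that symptom improved.

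**Working it through.** The plan gives no figure on this point to reproduce. The check sets the contacts side by side and then does the schedule arithmetic.

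**Contacts compared (section 5.1 with Table 1, and 5.5)**

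| Contact | General ascertainment | B/F/TAF-specific inquiry |
|---|---|---|
| Baseline (Day 0) | Symptom assessment, interim history, stability check, AE monitoring; side-effect education | No |
| Day 14 call | Changes in history and medication, AE monitoring | No |
| Day 45 visit | Symptom assessment, interim history, stability check, AE monitoring; education repeated | No |
| Day 126 call | Changes in history and medication, AE monitoring | No |
| Day 168 visit | Symptom assessment, interim history, stability check, AE monitoring | **Yes** |
| Day 174 call | AE monitoring (Table 1 also marks history and medications) | No |

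The general layer is present throughout. The specific layer appears once, at the last visit on drug.

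**Timing**

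- Nominal gaps between contacts: 14 − 0 = 14; 45 − 14 = 31; 126 − 45 = 81; 168 − 126 = 42; 174 − 168 = 6 days.
- First call after the switch, with its 7-day window: Day 7 to Day 21.
- Longest gap with windows (Day 45 ± 14, Day 126 ± 7): (126 + 7) − (45 − 14) = 133 − 31 = 102 days.
- Day 0 to the only specific inquiry: 168 days (± 7).
- If the same inquiry were made at every contact from Baseline, the longest nominal interval between inquiries would be 81 days instead of 168, and a pre-switch answer would exist.

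**Who may not be asked**

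Section 6.2 expects about 15% attrition between the two PET scans: 0.15 × 30 = 4.5, so 4 to 5 of 30. Table 1 has no early-termination visit, and section 9.3 lists an intolerable adverse event among the reasons for discontinuation. The inquiry therefore sits where only patients who reach Day 168 are sure to receive it.

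**How a carried-over symptom would be classified**

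Under 9.4.3 a symptom with a reasonable time sequence that other drugs or disease could also explain is graded possible, and its relationship to study drug then counts as not ruled out. The same table would also allow it to be graded not related. Without a baseline answer or an onset date, little in the record settles which applies.

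**Leverage of one patient**

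1/30 = 3.3 percentage points. For scale only, Table 3 reports nausea in 10%, headache in 11% and diarrhea in 13% on B/F/TAF; applied to 30 patients these are 3.0, 3.3 and 3.9 patients.

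**The case against.** The best defense is that the plan already asks. Section 5.5 requires symptom assessment at Baseline and Day 45, staff call every patient at about two weeks specifically to look for adverse events, and patients are taught the side effects twice. The Day 168 inquiry is also part of a check of change since screening, so an unchanged symptom is not what it seeks. Section 6 plans no adverse-event rates and no comparison by visit, and nausea, diarrhea and headache are not among the safety end points in 9.1.

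Most of this stands, and it rules out three stronger readings that a reader might infer.

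- *That contacts before Day 168 rely on spontaneous reports alone.* Sections 5.1 and 5.5 contradict this, and 9.1 itself lists other sources.
- *That patients are asked nothing before the switch, or that early events are missed.* Baseline has a general symptom assessment. Early events have several routes to being recorded; the supportable claim is that mild ones may be under-recorded.
- *That the artefact is as large as the drug's own side-effect rate.* Supposing that 5–20% of 30 patients had an unvoiced long-standing symptom would give 1.5 to 6 patients, against 3 to 4 from Table 3. But 5–20% is a pure assumption, and such symptoms would also have to escape the Baseline assessment. It pools any symptom, whereas Table 3 gives incidence per symptom in treatment-naive adults, from trials that the reference list cites as week-48 results.

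The defense does not remove the difference in prompting. A general assessment is not the same question as a product-specific one, teaching patients what to expect is not asking what they already have, and no written rule separates old symptoms from new.

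**Conclusion.** The point holds in a limited form. The specific inquiry is written for one contact of six, with no matching answer on the old regimen, and 5.5 and 9.1 describe symptom ascertainment at the same visits differently. Uneven prompting can move common, non-serious symptoms into or out of the on-drug count.

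The damage is confined to descriptive rates of those symptoms. The CFR primary endpoint is untouched. The 9.1 end points (death, death or cardiovascular hospitalization, symptomatic arrhythmia, drug-related serious events and significant laboratory abnormalities) do not depend on this inquiry.

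Neither the size nor the net direction can be derived from the documents: carried-over symptoms would inflate the count, while unrecorded early ones and patients who stop would deflate it. The conclusion assumes that staff follow the written lists and that common adverse events will be described in the report, which section 6 does not state. It is a modest improvement, worth making because it is cheap and a pre-switch answer cannot be reliably recovered later.

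**What to change.** 1. In 5.1, add one short scripted inquiry covering nausea, diarrhea and headache, the symptoms named in 7.4. Use it at Baseline before the first B/F/TAF dose and in the same words at Days 14, 45, 126, 168 and 174. Use the script in place of the unspecified Day 168 inquiry, so that all four sites ask the same thing.
2. Ask the same questions at the last contact of anyone who stops early.
3. Record the onset date and whether each symptom is new or worse than the Baseline answer. Add to 9.4.1 that a symptom present and unchanged since Baseline is not counted as arising on B/F/TAF.
4. Flag prompted and volunteered reports separately, so that either can be tabulated alone.
5. Reconcile 5.5 with 9.1 so that both describe the same method at visits.

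The scheduled contacts already exist. The cost is a short edit, a few minutes per contact and a few more mild events on record. In return, symptoms are ascertained evenly, and early intolerance is more likely to be noticed at the first call.
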